**NCT03983434**

**October 4, 2022**

## Fecal bile acids, fecal short chain fatty acids and the intestinal microbiota in patients with irritable bowel syndrome (IBS) and control volunteers: Diet Challenge

Patients with irritable bowel syndrome (IBS) may exhibit atypical profiles of intraluminal bile acids and short chain fatty acids (SCFA). Intraluminal bile acids may influence intestinal secretion, permeability, transit, motility and visceral hypersensitivity. Bile acid sequestration, administration, and modulation of bile acid synthesis have shown promising effects on stool characteristics, colonic transit and symptoms during treatment of chronic diarrhea and constipation. Intraluminal SCFA may also exert important effects on intestinal fluid and electrolyte absorption, motility and symptoms in IBS. Altered SCFA profiles have been identified in IBS, although the pattern of these alterations is incompletely understood. Identifying the underlying mechanisms that drive differences in intraluminal bile acids and SCFA could be critical to understanding the pathogenesis of IBS.

There is emerging evidence that alterations in bile acids and SCFA associated with IBS could be associated with changes in the gut microbiota. In addition to modulating levels of intraluminal organic acids, it has been hypothesized that gut microbiota may alter local immune responses, modulate visceral pain responses, and impair gut barrier function. Our **overall goal** is to investigate the relationship between fecal bile acids, SCFA and the gut microbiota in IBS. Results of this pilot study could reveal insights into the interplay of the gut microbiota and small molecule mediators of IBS to suggest targeted clinical strategies for improved diagnosis and management of this important syndrome.

**SPECIFIC AIMS & HYPOTHESIS:** The central hypothesis of this proposal is that specific shifts in the GI microbiome composition correlate with altered colonic SCFAs and BAs and contribute to IBS symptoms

**Specific Aim 1:** Identify GI microbiome signatures in IBS subtypes (IBS-C and IBS-D) and matched controls, and test if microbiome signatures in these groups correlate with fecal SCFAs and bacterial fermentation of an indigestible carbohydrate (inulin) after a dietary challenge (fecal inulin).

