**Aim 1a Hypothesis:** Abundance of specific SCFA-producing bacterial taxa (e.g. clostridial clusters IV and XIVa) correlates with fecal SCFAs and will distinguish IBS-C from IBS-D and IBS subtypes from controls.

**Aim 1b Hypothesis:** Abundance of specific SCFA-producing bacterial taxa is inversely correlated with fecal inulin and will distinguish IBS-C from IBS-D and IBS subtypes from controls.

**Specific Aim 2:** Determine if GI microbiome signatures in IBS subtypes and controls correlate with fecal BAs or markers of SCFA production (fecal SCFAs or inulin) and test if BAs correlate with fecal SCFAs or inulin.

[figure not shown]
**Aim 1b Hypothesis:** Abundance of BA-dehydroxylating taxa (e.g. genus *Clostridium*) correlates with decreased total fecal BAs in IBS-C and increased total fecal BAs in IBS-D compared to controls.

**Aim 2b Hypothesis:** Abundance of BA-dehydroxylating taxa is associated with fecal SCFAs and fecal inulin.

**Aim 2c Hypothesis:** Fecal inulin and SCFAs differ in IBS-D patients with and without BA malabsorption.

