**Statistical considerations:**

The primary endpoints for analysis will be:

- 1) Total bile acid excretion
- 2) Total and individual fecal excretion of SCFA
- 3) Fecal microbial population
- 4) Fecal inulin

The secondary endpoints for analysis will be:

- 1) Percent primary fecal bile acid excretion
- 2) Stool characteristics (frequency, consistency, ease of passage) based on bowel diary

The associations of fecal SCFAs (continuous variable) with phenotype (using HV as the reference group) and specific microbial taxa will be assessed using a general linear model (GLM) adjusting for relevant covariates. The relative abundance of specific bacterial taxa will be measured and compositional data analysis will be performed to assess the associations of relative microbial taxa abundances with fecal SCFAs or other endpoints (fecal inulin) and to assess whether phenotype alters observed associations. GLM will include specified endpoints, phenotype, the interaction between the endpoint of interest and phenotype, and relevant covariates as prediction variables for SCFAs or other endpoints of interest. False discovery rate (FDR) control will be performed using the Benjamini-Hochberg procedure to correct for multiple testing. We will explore (a) multivariable associations between overall community composition (e.g. Bray-Curtis dissimilarity) with phenotype, fecal SCFAs, or fecal inulin using the PERMANOVA approach adjusting for covariates and (b) the influence of bowel functions on the association between microbial endpoints with fecal SCFAs or inulin in IBS.

Associations of total fecal bile acids with relative abundance of microbial taxa and other specified endpoints (fecal SCFAs or inulin) will be assessed using GLM adjusting for covariates. FDR control will be performed using the Benjamini-Hochberg procedure. Among IBS-D participants, we will test associations between fecal SCFAs or inulin and bile acid phenotype (with or without bile acid malabsorption) using ANCOVA adjusting for covariates. We will explore (a) multivariable associations between overall community composition (Bray-Curtis dissimilarity) with phenotype or total fecal bile acids using the PERMANOVA approach adjusting for covariates and (b) associations between primary fecal bile acids with relative microbial abundances in IBS patients.

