**Sample size and Power:** We will enroll 24 patients with IBS-D, 24 patients with IBS-C, and 24 healthy controls. In order to compensate for withdrawals and loss to follow-up, up to 50 patients could be enrolled to meet the 24 studied in each group.

Sample size assessment is based on results of primary endpoints for Aim 1 from a preliminary dataset acquired by our lab and calculated using ANOVA among three cohort groups. We will have 80% power at the 5% significance level to detect the effect size shown in the table for fecal SCFAs between 19 IBS-C, 19 IBS-D, and 19 HV. Estimated effect sizes for other endpoints of interest are shown in the Table.

Table: Estimated effect sizes

Response (Data show mean+SD)	HV	IBS-C	IBS-D	Effect size (cohen's f)	N per group
Relative abundance of clostridial cluster IV (%)	0.181+0.221	0.392+0.354	2.01+4.06	0.39	22
Relative abundance of clostridial cluster XIVa (%)	0.0814+0.148	0.04+0.0316	0.137+0.31	0.181	99
Relative abundance of genus Clostridium (%)	0.486+0.368	0.84+0.647	2.57+3.85	0.461	16
Overall colonic transit (days)	1.55+0.977	1.52+1.39	1.08+0.649	0.461	65
Total SCFA excretion (µg/mg)	9.94+5.87	16.5+10.1	11.5+2.9	0.235	19

**Inclusion of Women, Minorities, and Children:** Individuals will not be excluded based on gender, race, or ethnicity. Patients with irritable bowel syndrome are comprised of both men and women and have diverse racial and ethnic backgrounds. The prevalence of irritable bowel syndrome among white, blacks, and Hispanics in the U.S. is very similar. Gender and racial/ethnic differences in fecal bile acid and SCFA excretion have not been reported. The communities of Marion County are anticipated to be 65% white, 29% black or African American and 6% other minorities. Children, 18-21 years of age, and adults 21 years or older will be eligible for participation in the study as active participants. However, children below 18 years of age will be excluded.

**Hazardous Procedures, Situations, or Materials and Protection of Human Subjects:** Potential exposure to radiation will be recognized. A Data Safety Monitoring Plan will be proposed. Participant records will have a unique identifier and other identifier information, including name, address, email, home address will be deleted. Only de-identified or anonymized clinical data will be transferred to processing laboratories.

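### Aims 1a and 1b say taxa will separate IBS-C from IBS-D, but the analysis plan has no model of taxon abundance by phenotype and names no direct IBS-C versus IBS-D contrast

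*Combined protocol and SAP*

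**What the plan says.** Under Specific Aims & Hypothesis, Specific Aim 1 is to "Identify GI microbiome signatures in IBS subtypes (IBS-C and IBS-D) and matched controls". Aim 1a states that abundance of SCFA-producing taxa, with clostridial clusters IV and XIVa as examples, "correlates with fecal SCFAs and will distinguish IBS-C from IBS-D and IBS subtypes from controls". Aim 1b (the inulin hypothesis under Specific Aim 1; the same label is used again under Specific Aim 2) states that abundance "is inversely correlated with fecal inulin and will distinguish IBS-C from IBS-D and IBS subtypes from controls". Each hypothesis makes two claims: abundance is correlated with a metabolite, and abundance separates the groups.

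Under Statistical considerations, the microbial population is the third primary endpoint. The Aim 1 analyses are:

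- a model in which associations of fecal SCFAs "with phenotype (using HV as the reference group) and specific microbial taxa will be assessed using a general linear model (GLM", with covariates;
- compositional analysis of taxa against SCFA or inulin, "and to assess whether phenotype alters observed associations". The model statement reads "GLM will include specified endpoints, phenotype, the interaction between the endpoint of interest and phenotype, and relevant covariates as prediction variables", with SCFAs or other endpoints as the outcome;
- Benjamini-Hochberg control of the false discovery rate;
- as exploration, PERMANOVA of overall community composition on phenotype, SCFA or inulin.

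Under Sample size and Power, sample size was "calculated using ANOVA among three cohort groups". The 80% power statement is for fecal SCFAs. The table also gives effect sizes for cluster IV, cluster XIVa and genus *Clostridium* as other endpoints of interest.

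**The concern.** Separating the subtypes is a stated hypothesis, and recruitment is limited to IBS-D and IBS-C so that the extremes of the phenotype are studied. Yet none of the listed analyses asks whether a named taxon is more or less abundant in IBS-C than in IBS-D. For SCFA and inulin, the contrasts that a model referenced to HV reports by default are IBS-C minus HV and IBS-D minus HV.

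Without a named subtype contrast, the easiest route to a subtype statement is to note that one subtype differs significantly from HV and the other does not. That is not a test of the difference between subtypes. It can suggest a difference where none exists, and it can miss a real one when the subtypes lie on opposite sides of HV.

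**Working it through.** **1. Hypothesis against analysis.**

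| Claim in Aims 1a and 1b | Analysis that addresses it |
|---|---|
| Taxon abundance correlates with SCFA or inulin | GLM and compositional analysis |
| That correlation differs by phenotype | Interaction term (slopes) |
| Community composition differs by phenotype | PERMANOVA, exploratory, not taxon-specific |
| A named taxon's abundance differs, IBS-C versus IBS-D | None |
| SCFA or inulin differs, IBS-C versus IBS-D | Not named; computable from the GLM |

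The interaction cannot stand in for the fourth row. Two groups can have the same taxon-SCFA slope and very different abundances, or the reverse.

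**2. Does HV coding block the contrast?** No. With a three-level factor, IBS-C minus IBS-D is the difference between the two HV-referenced coefficients. On one simulated data set with 24 per group, that difference from an HV-referenced interaction model gave the same t-values as refitting with IBS-D as reference: 2.505 for the phenotype term and -0.609 for the interaction.

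**3. The plan's own sample-size figures for taxa.** One-way ANOVA, three groups, 5% level, 80% power, at the printed Cohen's f:

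- cluster IV, f = 0.39: 22.1 per group (printed 22);
- cluster XIVa, f = 0.181: 99.0 (printed 99);
- genus *Clostridium*, f = 0.461: 16.2 (printed 16).

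These reproduce within rounding, so a three-group comparison of abundance was costed. The SCFA row does not reproduce (f = 0.235 needs 60 per group, not 19). That is a separate matter and does not affect this point.

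**4. Size of the inference problem.** Assumptions: normal data, 24 per group, pooled-variance t tests on 69 df, unadjusted 5% level, IBS-C and IBS-D identical and both shifted d SD from HV.

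| d from HV | Exactly one subtype significant against HV |
|---|---|
| 0.2 | 14% |
| 0.5 | 32% |
| 0.6 | 33% |
| 0.7 | 30% |
| 0.8 | 24% |
| 1.0 | 10% |
| 1.2 | 3% |

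The direct contrast rejects in 5% throughout. In the opposite case, with the subtypes at +0.4 and -0.4 SD from HV, neither HV comparison is significant in about 47% to 48% of trials, while the direct contrast detects the difference in 78%.

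**5. Power of the direct contrast.** Inputs are the means and SDs in the sample-size table. d = |mean C - mean D| / sqrt((SD C² + SD D²)/2). Power is from a two-sided 5% t test with 24 per group. The n for 80% power is 2(1.96 + 0.842)²/d², about 15.7/d².

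| Endpoint | Difference / SD | d | Power at 24 | n per group for 80% |
|---|---|---|---|---|
| Cluster IV | 1.618 / 2.882 | 0.56 | 48% | 50 |
| Cluster XIVa | 0.097 / 0.220 | 0.44 | 32% | 81 |
| Genus *Clostridium* | 1.73 / 2.761 | 0.63 | 57% | 40 |
| Total SCFA | 5.0 / 7.430 | 0.67 | 63% | 35 |

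With the SD pooled over all three groups (normal approximation), the powers are 66%, 39%, 75% and 70%. None reaches 80%, before any FDR adjustment.

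**The case against.** The strongest reply is that the plan already covers this: phenotype and its interaction are in the GLM, PERMANOVA is run on phenotype, and the tabulated three-group effect sizes show that an abundance comparison was intended. Part of this stands. A reader might infer that the plan has no taxon-by-phenotype term, that phenotypes can be compared only with HV, or that the subtype objective cannot be tested. The documents support none of these. The interaction is explicit, HV is named as reference once (for the SCFA model), and that coding leaves the subtype contrast available. What fails is the step from intended or computable to planned: for taxon abundance no planned GLM clearly exists from which to take the contrast.

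A generous reader could count the microbial population among the other endpoints the GLM may take as outcome. Phenotype would then be adjusted for a metabolite and its interaction, which is not a comparison of abundance, and the subtype contrast would still be unnamed.

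Three further limits are fair. The plan nowhere says it would infer a subtype difference from discordant HV comparisons, and the rates in step 4 use unadjusted tests although the plan applies Benjamini-Hochberg. The rates also peak near 0.6 SD and fall away on either side. Nor should the table be read as sizing the study on taxa: the power claim is for SCFA, and cluster XIVa is listed at 99 per group against 24 planned.

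It is also tempting to say that the unnamed contrast is the largest. For SCFA it exceeds IBS-D versus HV (d = 0.67 against 0.34) but not IBS-C versus HV (0.79). For cluster IV (0.72, 0.64 and 0.56 for C-HV, D-HV and C-D) and genus *Clostridium* (0.67, 0.76 and 0.63) it is the smallest of the three. Only for cluster XIVa is it the largest.

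**Conclusion.** The point holds as a mismatch between objective and analysis. The hypotheses say that taxa separate IBS-C from IBS-D; the analysis section models no named taxon's abundance by phenotype and pre-specifies no direct subtype contrast for SCFA or inulin. The sample-size table tabulates a three-group abundance comparison that the analysis section does not contain.

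Its size is conditional. If discordant HV comparisons were used as evidence, the error for identical subtypes would be 24% to 33% at 0.5 to 0.8 SD from HV and lower outside that range, against 5% for the direct contrast. This assumes normal data, equal variances and no FDR adjustment. The 32% to 63% power for the direct contrast is approximate: the tabulated SDs are very unequal (0.354 and 4.06 for cluster IV), abundances are likely to be skewed, and covariates and log-ratio transformation are not reflected. In a study that calls itself a pilot, this should be corrected before analysis, and wording is enough to do it.

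**What to change.** Add to Statistical considerations:

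1. For clostridial clusters IV and XIVa, a model of log-ratio-transformed abundance on three-level phenotype, adjusted for the listed covariates (age, BMI, sex, acid suppression). Genus *Clostridium* is named under Specific Aim 2 for bile acids, without a claim to separate the subtypes, so including it is optional.
2. From that model and from the SCFA and inulin GLMs, the direct IBS-C minus IBS-D contrast with its 95% CI, beside the two HV contrasts and in the same Benjamini-Hochberg family. Where the interaction is in the model, state the taxon value at which the contrast is taken.
3. A rule that any statement that a marker distinguishes IBS-C from IBS-D rests on this contrast, and not on one subtype differing from HV while the other does not.

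No new data are needed. The cost is a slightly larger FDR family and a contrast with limited power: about 32% to 63% at pilot effect sizes with 24 per group before FDR. The plan should therefore say that a non-significant contrast will be interpreted from its confidence interval and not reported as no difference.

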## SIGNIFICANCE

*Primary fecal BA significantly higher in IBS-D and non-secretory BA (LCA) higher in IBS-C*

Shin A et al. Clin Gastroenterol Hepatol. 2013;11:1270-1275.e1.

**Mechanistic effects of bile acids in pathogenesis of Irritable Bowel Syndrome** Despite its global prevalence and impact on quality of life, current therapeutic options and actionable biomarkers for the treatment of IBS are limited. Bile acid malabsorption is identified in up to 50% of patients with functional diarrhea or diarrhea-predominant IBS (IBS-D). Clinical studies have shown increased primary fecal bile acids, cholate and chenodeoxycholate, in IBS-D and increased non-secretory secondary bile acids, lithocholate, in constipation-predominant IBS (IBS-C). The effect of bile acids on colonic mucosa is in part, determined by bile acid chemistry. Chenodeoxycholate and deoxycholate have been

associated with increased fluid secretion, intestinal permeability and mucosal damage. Stimulation of propagated pressure waves has been shown in the proximal human colon with intraluminal chenodeoxycholate. In mice, deoxycholate induces peristalsis through TGR5-mediated effects. Administration of chenodeoxycholate or elobixibat, an inhibitor of the ileal bile acid transporter, in patients

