**Relationship between intestinal microbiota and intraluminal organic acids** Bile salt hydrolases from several intestinal bacterial species including *Bacteroides*, *Clostridium perfringens*, *Bifidobacterium*, *Lactobacillus* and *Listeria monocytogenes* deconjugate bile acids. Both conjugated and deconjugated bile acids have been shown to induce intestinal secretion. Although the physiologic advantages of deconjugation are incompletely understood, there is evidence that bile salt hydrolases aid in bacterial colonization of the lower GI tract, promote detoxification of bile salts and increase resistance to bile salt toxicity. Free bile acids rapidly undergo dehydroxylation by intestinal bacteria, converting primary to secondary bile acids. This metabolic pathway is found in ~0.0001% of total colonic flora and the bacteria capable of dehydroxylation have previously been classified as *Clostridium*. Changes in fecal metabolite profiles leading bowel dysfunction and symptoms in

IBS may reflect underlying shifts in the fecal microbial community. Alternatively, alterations in underlying gut physiology such as transit may contribute to the development of dysbiosis, suggesting a bi-directional interaction. It has been hypothesized that an observed decline in anaerobes following acute gastroenteritis may be a consequence of accelerated transit resulting in a loss of the anaerobic niche, and loss of the bacteria required for carbohydrate fermentation to SCFA. Theoretically, accelerated transit may also reduce the time available for bacterial transformation of bile acids. Further investigation of the relationship between fecal microbiota and changes in the metabolome (e.g. bile acids and SCFA) is required for continued development of diagnostic and therapeutic strategies in IBS.

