**Data analysis of molecular methods:**

16S sequencing data will be processed by the DADA2 package to generate separate lists of microbial taxa and their relative abundances in stool. For downstream biostatistical analysis, to minimize unequal sampling effects, 16S sequences from each individual will be sub-sampled to equal sequencing depth. Using the statistical R packages, *phyloseq* and *vegan*, bacterial taxa richness and α/β diversity indices.

**SCFA and bile acid measurement:** The stool sample submitted by study participants will be split at the lab for DNA isolation and frozen aliquots will be shipped to the Metabolite Profiling Facility at Purdue University and the Mayo Clinic Department of Laboratory Medicine and Pathology for SCFA and bile acid measurement respectively. Total and individual fecal bile acid excretion will be measured by high-performance liquid chromatography/tandem mass spectrometry (per 48 hours on a 100 g fat diet). Analysis and analytical performance have previously been documented. The lower limit of quantitation of each of the individual measured BAs is 0.06 μmol (in methanol extract). Measurement of SCFA will be performed by liquid chromatography-mass spectrometry using previously published methods.

[figure not shown]
**Fecal inulin content** will be measured using short acid hydrolysis and high-performance liquid chromatography to measure inulin as hydroxymethylfuraldehyde by the Complex Carbohydrate Research Center at the University of Georgia. This approach is adapted from a method that has previously been published to measure inulin in plasma and urine.

Inulin (Orafti®) is officially recognized by The United States Food and Drug Administration as an approved dietary fiber. This fiber occurs naturally in a great number of plants and vegetables. Orafti® inulin is extracted through hot water processing and is of 100 % vegetable origin. In order to minimize any potential symptom exacerbation that may occur with consumption of such a dietary fiber, inulin supplementation will be limited to a one-time ingestion of a 10 gram dose.

**Stool Frequency and Consistency:** Participants will complete a validated daily diary to record bowel habits (frequency, consistency and form). Participants will be given the option of completing the diary on paper, which will be dispensed at Visit 1 and collected at study conclusion.

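### The only taxon analysis of primary bile acids, the pool that dehydroxylation acts on, is exploratory and leaves out the controls

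*Combined protocol and SAP*

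**What the plan says.** The first hypothesis under Specific Aim 2 (printed as Aim 1b) begins "Abundance of BA-dehydroxylating taxa (e.g. genus" and names genus Clostridium as the example. It states that this abundance "correlates with decreased total fecal BAs in IBS-C and increased total fecal BAs in IBS-D compared to controls".

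The Significance section, on the relationship between microbiota and intraluminal organic acids, describes the process: "Free bile acids rapidly undergo dehydroxylation by intestinal bacteria, converting primary to secondary bile acids".

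Under Statistical considerations, the primary bile acid endpoint is "Total bile acid excretion" and the first secondary endpoint is "Percent primary fecal bile acid excretion". The main bile acid model is a covariate-adjusted GLM of the total on taxa and on the other endpoints, with Benjamini-Hochberg control and no restriction to IBS. The link between taxa and primary acids appears only as item (b) of the exploratory sentence that closes the bile acid paragraph: "associations between primary fecal bile acids with relative microbial abundances in IBS patients".

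The data needed for more are planned. Stool is collected from all participants (Sample collection), and "Total and individual fecal bile acid excretion will be measured by high-performance liquid chromatography/tandem mass spectrometry".

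**The concern.** The hypothesis picks its taxa by a function, dehydroxylation, whose direct product is a change in composition. The outcome it names, and the main model, use the sum. The endpoint closest to the function is percent primary. It has no model stated by name, and the one analysis near it omits the group against which the hypothesis is framed.

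The interpretation of the dehydroxylation aim is at stake. If the plan is followed as written, the paper will hold an FDR-controlled result on the total, which several processes can move, and an exploratory result on primary acids with no healthy reference. Neither would show whether the relation between these taxa and the primary/secondary split differs between IBS and health. The protocol's own background also places the IBS signal in composition: "Primary fecal BA significantly higher in IBS-D and non-secretory BA (LCA) higher in IBS-C". That is a group difference, not a taxon association, but it supports giving the split a proper model.

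**Working it through.** The plan gives no sample size or power for any bile acid endpoint, so there is no stated figure to reproduce. The check is mainly one of setting the text side by side; the arithmetic is illustrative.

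1. **Direct effect of conversion.** Let P and S be the primary and secondary amounts in moles, and T = P + S. If an amount c is converted one for one, P becomes P − c and S becomes S + c. Then T is (P − c) + (S + c) = P + S, unchanged, while percent primary falls from 100·P/T to 100·(P − c)/T. This is an inference from the protocol's description and covers the direct effect only.

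2. **Other routes.** The Significance section reports bile acid malabsorption in as many as half of patients with functional diarrhea or IBS-D. It allows a two-way relation between transit and the microbiota, and suggests that faster transit may leave bacteria less time to transform bile acids. A taxon could therefore track the total without dehydroxylation being the reason. Transit may also shift the split, so percent primary is the more direct measure but not a pure one.

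3. **Analysis populations.** From Sample size and Power: 24 IBS-D + 24 IBS-C + 24 controls = 72, of whom 48 have IBS.

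4. **Detectable correlation.** Fisher z, two-sided 5%, 80% power, one unadjusted pooled correlation: r = tanh[(1.960 + 0.842)/√(N − 3)].
   - N = 72: 2.802/8.307 = 0.337, so r = 0.325.
   - N = 48: 2.802/6.708 = 0.418, so r = 0.395.

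5. **Power over a range of assumed correlations.** Φ(atanh(r)·√(N − 3) − 1.960):

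| True r (assumed) | N = 72 | N = 48 |
|---|---|---|
| 0.30 | 73% | 55% |
| 0.35 | 86% | 69% |
| 0.40 | 94% | 81% |

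6. **With multiplicity.** The number of taxa is not stated. Assume m taxa with one real association at r = 0.35, so that the first Benjamini-Hochberg threshold is 0.05/m:

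| m (assumed) | Threshold | N = 72 | N = 48 |
|---|---|---|---|
| 10 | 0.005 | 59% | 36% |
| 20 | 0.0025 | 50% | 28% |
| 50 | 0.001 | 40% | 20% |

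7. **Difference from controls.** On the Fisher z scale, 24 controls against 48 IBS patients gives SE = √(1/21 + 1/45) = 0.264. If r is 0 in controls, 80% power needs r = tanh(2.802 × 0.264) = 0.63 in IBS; at r = 0.35 power is about 28%. For one subtype against controls, SE = √(1/21 + 1/21) = 0.309 and the required r is about 0.70.

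**The case against.** The strongest reply is that the model tests what the hypothesis says. The hypothesis is an association with the total, in opposite directions in IBS-C and IBS-D. Simple conversion would not predict that pattern, so the claim concerns taxa identified by function rather than conversion lowering a sum. The total also has its own rationale, since the protocol treats altered bile acid excretion as a validated biomarker. This is a self-described pilot, and ranking the total above percent primary is a legitimate choice. All of this stands.

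Three stronger readings are tempting, and the documents do not support them.

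- A reader might infer that the total bile acid model cannot detect anything relevant and that a null would be worthless. A null would still bear on the hypothesis as written. The documents nowhere say that the total is unaffected by these taxa, and they leave indirect routes open. Simulating a total set independent of the taxon would only return that assumption.
- A reader might infer that the primary-acid measure is merely exploratory. Percent primary is a listed secondary endpoint; its association with taxa is what is exploratory. The exploratory wording also does not say whether it means percent or absolute amounts.
- A reader might infer that adding controls restores good power. Steps 6 and 7 show otherwise. The published abundances are also skewed and shifted between groups (genus Clostridium 2.57 with SD 3.85 in IBS-D, 0.486 with SD 0.368 in controls), which a pooled correlation does not reflect.

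The gap remains after these points: no reason is given for omitting controls from the one taxon analysis closest to dehydroxylation.

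**Conclusion.** The point holds as a gap in the analysis plan that is cheap to close. The test of the total agrees with the stated hypothesis, but its result, positive or null, cannot alone be attributed to dehydroxylation. Percent primary has no analysis stated by name, and the taxon analysis of primary acids is exploratory and confined to 48 of 72 participants, although the hypothesis is framed against controls.

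The size is modest. Using all 72 lowers the detectable correlation from about 0.395 to 0.325, for one unadjusted correlation before covariates and FDR control. The larger gain is that a comparison with controls becomes possible at all, though only large differences would be detected. The conclusion assumes one-for-one conversion as the direct effect and that individual acids are assayed in all three groups, as the measurement section implies by stating no restriction. The validity of the trial is not in question.

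**What to change.** In the bile acid paragraph of Statistical considerations, add a GLM with percent primary (or the log primary-to-secondary ratio) as response and the dehydroxylating taxa as predictors, in all three groups. Include phenotype with healthy volunteers as reference, the taxon-by-phenotype interaction and the stated covariates, and place it inside the Benjamini-Hochberg family. List the taxa in advance, since the plan gives only an example, and say whether primary acids are analysed as a percentage or an amount.

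Keep total bile acids as the excretion endpoint, and base any statement about dehydroxylation on the primary/secondary model, noting that transit may also affect the split.

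The cost is wording plus one more response in the FDR family. No new assay, visit or participant is needed. The interaction will be imprecise at 24 per group, so report it with confidence intervals and do not read a non-significant interaction as evidence of no difference.
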